### Subject Record at Follow-up

#### Participant questionnaire – PQi and GQi Evaluation Questionnaire

##### Part I

Do you have a history of **catching** a cold\* (\*, defined by TCM) in the past year? If no, please proceed to Part II of this section; if yes, please fill out the following blanks.

1. How many times did you **catch** a cold\* in the **past year**?

i. Once

duration:

ii. Twice

duration of cold #1:

duration of cold #2:

iii. 3 times or more

duration of cold #1:

duration of cold #2:

duration of cold #3:

duration of other colds:

iv. During the above colds\*, did you experience any of the following symptoms:

- Sneezing
- Coughing
- Sweating
- Nasal discharge or congestion
- High fever (body temperature  $> 39.1^{\circ}\text{C}$ )
- Itching or painful throat
- Headache
- Aversion to wind and cold
- General pain and malaise

2. How many times did you **catch** a cold\* **last winter (2017 – 2018)**?

i. Once

duration:

ii. Twice

duration of cold #1:

duration of cold #2:

iii. 3 times or more

duration of cold #1:

duration of cold #2:

duration of cold #3:

duration of other colds:

iv. During the above colds\*, did you experience any of the following symptoms:

- Sneezing
- Coughing
- Sweating
- Nasal discharge or congestion
- High fever (body temperature > 39.1C)
- Itching or painful throat
- Headache
- Aversion to wind and cold
- General pain and malaise

3. How many times did you **catch** a cold\* in the **last two months**?

i. Once

duration:

ii. Twice

duration of cold #1:

duration of cold #2:

iii. 3 times or more

duration of cold #1:

duration of cold #2:

duration of cold #3:

duration of other colds:

iv. During the above colds\*, did you experience any of the following symptoms:

- Sneezing
- Coughing
- Sweating
- Nasal discharge or congestion
- Itching or painful throat
- Headache
- Aversion to wind and cold
- General pain and malaise
- High fever (body temperature > 39.1C)

## Part II

- a. Do you have spontaneous perspiration? I don't readily sweat, or sweat only with intense physical activities
  - b. I sweat with some slight physical activities like walking
  - c. I sweat spontaneously
  - d. I sweat heavily and instantly with physical activities
  - e. I sweat even without any physical activities
4. Aversion to wind or cold
- a. No aversion to wind or cold
  - b. Aversion to wind
  - c. Aversion to cold, but relieved by adding clothing
  - d. Aversion to both cold (but relieved by clothing) and wind, or susceptible to cold\* when exposed to wind or cold weather
  - e. Aversion to cold (only relieved by clothing that covers whole body), very readily catch a cold\* when exposed to wind or cold weather

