# Attachment I: Insufficiency of Protective Qi (IPQ) Index

Final score	Subscore C	Subscore B	Subscore A		
IPQ index, Weighted sum of Subscore Cs. Part I Wt.: 25%, Part II Wt.: 33.3%, Part III Wt.: 41.7%	Part I: Score of Cold History, Weighted sum of Subscore Bs. Ia1 Wt. 66.7%, Ia2 Wt. 33.3%	Part Ia1: Cold* frequency (in the past 2 month & recovery (total time if $\geq$ once), select from Subscore As one that applies	no Cold* at all	1	
			Once & recovered within 3day	2	
			Once & recovered within 1wk	3	
			Once & recovered within 2wk	4	
			Once & recovered $\geq$ 2 wk	5	
			Twice & recovered within 3day	6	
			Twice & recovered within 1wk	7	
			Twice & recovered within 2wk	8	
			Twice & recovered $\geq$ 2 wk	9	
			3 time or more	10	
		Part Ia2: Cold* related symptoms; Sum of Subscore As + 1	Sneezing	1 if yes	
			Coughing	1 if yes	
			Sweating	1 if yes	
			Nasal discharge or congestion	1 if yes	
			Itching or painful throat	1 if yes	
	Headache		1 if yes		
	Aversion to wind and cold		1 if yes		
	General pain and malaise		1 if yes		
	Part II, Score of Other IPQ symptoms, Weighted sum of Subscore Bs. Ib1 Wt. 50%, Ib2 Wt. 50%	Part IIa: Spontaneous sweating, Select from Subscore As one that applies	High fever ( $\geq$ 39.10C)	1 if yes	
			Don't readily sweat, or sweat only with intense physical activities	1	
			sweat with some slight physical activities like walking	2	
			Sweat spontaneously	3	
			Sweat heavily and instantly with physical activities	4	
		Part IIb: Aversion to wind or cold, Select from Subscore As one that applies	Sweat even without any physical activities	5	
			No aversion to wind or cold	1	
			Aversion to wind	2	
			Aversion to cold, but relieved by adding clothing	3	
			Aversion to both cold (but relieved by clothing) and wind, or susceptible to cold* when exposed to wind or cold weather	4	
			Aversion to cold (only relieved by clothing that cover whole body), very readily catch a cold* when exposed to wind or cold weather	5	
			Part III: Sign Score, Weighted sum of Subscore As. of Part I- IV; Part I Wt. 24%, Part II Wt. 40%, Part III, 20%, Part IV, 16%		Part I: weak or powerless pulse
Part II: chun-pulse superficial or weak					Scale 1-5
Part III: corpulent tongue or with white fur					Scale 1-5
Part IV: low voice					Scale 1-5

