Enrollment will be initiated by a TCM practitioner. Note that the enrollment process may occur on the same day as the Screening Visit, or at a date not more than 14 days from the Screening Visit. If enrollment is performed on the same day as the screening visit, the enrollment process will begin with a basic physical examination (to be conducted by the Qualified Investigator, Q.I.; see Appendix 2) immediately following the screening process and continue as outlined below. Note that subjects that complete screening and enrollment on the same day will be considered to have completed both the Screening Visit and Study Visit 1. However, if subject enrollment cannot be completed during the Screening Visit (i.e., due to time restrictions or other circumstances), subjects will return to the clinic within 14 days to initiate the enrollment procedure. During this visit (Study Visit 1), the TCM practitioner will re-assess the subjects' PQD status (Appendix 4). If the potential subject does not exhibit PQD, they will not be enrolled in the study. If the potential subject continues to exhibit PQD, they will continue the

enrollment process. (Note that for purposes of data analysis, subjects' PQD status characterized during Study Visit 1 will supersede their PQD status characterized during the Screening Visit). As outlined above, the enrollment process begins with a basic physical exam of the head, ears, eyes, nose, throat, etc. performed by the Q.I. If, in the estimation of the Q.I., the potential subject is deemed not to be in good general health, they will not be enrolled in the study. If potential participants are deemed to be otherwise healthy by the Q.I., the enrollment procedure will continue. The enrollment will start in Dec. 2018 and concluded in March 2019.

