#### **9.4.2 Analysis of the Efficacy Endpoint(s)**

Trial outcome measures, if they are continuous, will be evaluated by skewness and kurtosis for normality and expressed as mean (95% CI) if both measures were within the range of (2, -2); otherwise they will be expressed as median (95% CI) with specification. Given the potential effect of treatment time on trial outcomes, we will analyze the effect of  $\beta$ -glucan with adjustment by treatment time. This will be conducted by linear mixed regression [16] or Aligned Rank Transformation ANOVA [17] if assumptions of the regression model were not satisfied. Categorical outcomes will be derived from conventional PQD diagnosis. The effect of  $\beta$ -glucan will be analyzed using generalized mixed linear model [18] for conventional PQD diagnosis.

For all statistical analyses, differences with a  $P < 0.05$  (two tailed) will be considered significant.

Other details analysis of the primary endpoints are described as follows:

- The PQi status of each participant at baseline and each follow-up visit will be measured by on-site investigators (licensed TCM practitioners) through a standardized quantitative assessment (Table 1 & Table 2). Each health condition relevant to PQD (i.e. cold frequency, symptoms, and signs) will be scored on a designed scale (ranging 1-10, with higher number indicating more severe deficiency) based on a set of standardized and specified criteria (Table 2). The sub-scores are then weighted (cold history 25%, symptoms 33.3%, signs: 41.7%) to arrive at a final PQD severity score. This score is on a 1-5 scale, with 5 being the most severe deficiency. The change of the score from baseline, indicating the treatment effect, will be calculated and analyzed by statistical means.
- PQi status of each participant at baseline and each follow-up visit will be measured by on site-investigators (licensed TCM practitioners) through non-standardized, qualitative traditional assessment. The status was characterized by non-PQD or PQD. The change of PQi status from baseline, indicating the treatment effect, will be calculated and analyzed by categorical statistic.

Other details analysis of the secondary endpoints are described as follows:

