**Table 2: Standardized criteria for PQi severity score assessment**

Candidate Parameter		Method of measurement and scores	
Cold Frequency	TCM Inquiry (Cold frequency)	No cold in the past 2 months	0
		Once in the past 2 months	1
		Twice in the past 2 months	2
		3 times or more in the past 2 months	3
Symptoms of PQD	TCM Inquiry (Spontaneous sweating)	No spontaneous sweating, sweat only with intense physical activities	0
		Sweat with routine physical activities	1
		Sweat heavily with routine physical activities	2
		Sweat with slight physical activities like walking	3
		Sweat spontaneously	4
	TCM Inquiry (Aversion to wind & cold)	No aversion to wind or cold	0
		Aversion to wind	1
		Aversion to cold, but relieved by adding light clothing	2
		Aversion to both cold (but relieved by light clothing) and wind, or susceptible to cold when exposed to wind or cold	3
		Aversion to cold (only relieved by thick clothing that covers whole body); or very easily catch a cold when exposed to wind or cold	4
Sign of PQD	TCM Auscultation (Low voice & apathy)	The participant's voice is loud & clear at a distance of 2m from the investigator	0
		The participant can be heard & understood at 2m from the investigator, but the voice is recognizably weak.	1
		The participant's voice is clearly low at 2m from the investigator & needs much attention to understand.	2
		The participant can be heard from 2m but need repeated clarification.	3
		The participant cannot be heard with a clear understanding at a distance of 2m.	4
	TCM Inspection (Tongue)	The tongue looks light red with thin white coating and is of proper size.	0
		The tongue looks pale in color with white coating; however, the tongue is of proper size & has no tooth mark on the sides.	1
		The tongue looks pale with white coating. This size is slightly larger than normal. Tooth-marks are visible but are limited to part(s) of the tip and sides of the tongue.	2
		The tongue looks pale with white coating. This size is significantly larger than normal. Tooth-marks are visible along the full length of the tip and sides of the tongue.	3
	TCM Palpation (Overall Pulse  )	Normal pulse	0
		Deficient Pulse is detectable but not apparent	1
		Apparent Deficient Pulse	2
	TCM Palpation (Cun Puls  )	Normal pulse	0
		The pulse shows characteristics of Floating or Deficient Pulse, but not both.	1
		Floating pulse is present, Deficient Pulse is detectable but not apparent.	2

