## Part VI

1. Do you often have poor appetite?
2. Do you have loose stools
3. Do you often have uncomfortable feeling in the abdomen after eating?

Part VII

1. Do you often feel palpitations?
2. Do you often feel depressed?

Part VIII

1. Do you have frequency of urination?
2. Do you often feel soreness of lower back?
3. Do you have cold limbs, especially legs?

Part IX

Score (Score each on a 1-5 scale)

5. weak or powerless pulse
6. cun-pulse superficial or weak
7. corpulent tongue or with white fur
8. low voice

# Appendix 5

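### The printed forms do not record the Table 2 levels that the primary PQD score and the 1.8 entry cut are calculated from, and no conversion rule is given

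*Combined protocol and SAP*

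**What the plan says.** **Scoring rule.** Section 9.4.2 has PQi status measured at baseline and every follow-up visit "through a standardized quantitative assessment (Table 1 & Table 2". Table 1 gives the weights and Table 2 the levels. Inclusion criterion 6 (Section 5.1) applies the same two tables to the >1.8 entry cut. Table 1 and Section 9.4.2 both put the final score on a 1-5 scale.

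**Forms.** Screening uses Appendix 1 (Section 5.5). For subjects who enrol on a later day, "the TCM practitioner will re-assess the subjects' PQD status (Appendix 4", and that result replaces the screening result for analysis. Appendix 4 is also the follow-up record.

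**Sweating.** Appendix 4, Part II lists five unnumbered options; the second is "I sweat with some slight physical activities like walking". In Table 2, "Sweat with slight physical activities like walking" scores 3, above "Sweat heavily with routine physical activities", which scores 2.

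**Signs.** Appendix 4, Part IX says "Score (Score each on a 1-5 scale" for both pulse items, tongue and voice, with no level descriptions. Table 2 has described levels: overall pulse 0-2, cun pulse 0-3, tongue 0-3, voice 0-4.

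**Screening form.** Appendix 1 rates the signs 1-10 and asks about colds over three months. Table 2 counts colds over two months.

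**The concern.** The plan names one instrument for the primary endpoint and binds in forms that collect another. Someone holding a completed Appendix 4 cannot reach a Table 1 and Table 2 score without choosing, item by item, how to turn form answers into levels, and the plan leaves those choices open. They affect the size of each participant's change. For sweating they can also affect its direction, because the two lists run in different orders.

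Entry is exposed as well. The cut of 1.8 is defined on the Table 2 score, but the screening form uses a third scale and a different recall period. Section 5.5 names Appendix 4 at Study Visit 1 only for subjects who return on a later day. As written, then, a same-day enrollee may have a baseline from Appendix 1 and follow-up from Appendix 4.

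**Working it through.** **1. The plan's own figure: a score range of 1-5.** Inputs are the Table 1 weights and the Table 2 lowest and highest levels.

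| Item | Weight | Table 2 levels | Appendix 4 |
|---|---|---|---|
| Cold frequency | 0.25 | 0-3 | count in last two months |
| Sweating | 0.167 | 0-4 | options a-e, different order |
| Aversion to wind and cold | 0.167 | 0-4 | options a-e, close match |
| Tongue | 0.083 | 0-3 | 1-5, undescribed |
| Voice | 0.067 | 0-4 | 1-5, undescribed |
| Overall pulse | 0.10 | 0-2 | 1-5, undescribed |
| Cun pulse | 0.167 | 0-3 | 1-5, undescribed |

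Minimum = 0. Maximum = 3(0.25) + 4(0.167) + 4(0.167) + 3(0.083) + 4(0.067) + 2(0.10) + 3(0.167) = 3.30. Adding 1 to every item gives 1.00 to 4.31. Attachment I of the Protocol gives 1.00 to 0.25(10) + 0.333(5) + 0.417(5) = 6.25. None of these reproduces 1-5.

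The 1.8 cut therefore has no fixed place:
- Tables 1 and 2 as printed: 1.8/3.30 = 54% of the range
- stated 1-5 scale: 0.8/4 = 20%
- Attachment I: 0.8/5.25 = 15%

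**2. Share of the score without a full mapping.** Tongue, overall pulse and cun pulse: 8.3 + 10 + 16.7 = 35.0%. Adding sweating: 35.0 + 16.7 = 51.7%. Voice (6.7%) also lacks a stated rule, although subtracting 1 would align 1-5 with 0-4. The weighted sign part runs 0 to 1.22 on Table 2 levels. If the form's 1-5 ratings were entered directly, it would run 0.42 to 2.09.

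**3. Sweating, option by option.** Position is counted from 0. Attachment I numbers the same options 1 to 5 in the same order, so changes are identical.

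| Appendix 4 option | By position | Nearest Table 2 level |
|---|---|---|
| a, intense exertion only | 0 | 0 |
| b, slight activity | 1 | 3 |
| c, spontaneous | 2 | 4 |
| d, heavy with activity | 3 | 2 (assumed) |
| e, no activity | 4 | 4 (assumed; no level of its own) |

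Table 2 level 1 (routine activity) has no form option. Weighted change = difference in level x 0.167:
- d to b: by position -2 x 0.167 = -0.33; by wording (3 - 2) x 0.167 = +0.17
- d to c: by position -1 x 0.167 = -0.17; by wording (4 - 2) x 0.167 = +0.33
- c to e: by position 2 x 0.167 = +0.33; by wording 0

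Of the 10 option pairs, two reverse, one ties under Table 2 and seven keep their direction. The reversals depend on where d is placed. With d at level 3, d to b becomes 0 and only d to c reverses (+0.17). With d at level 4, neither reverses.

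**4. What the form does match.** Attachment I has "Sweat heavily and instantly with physical activities" in fourth place and rates the signs 1-5, as Appendix 4 does. Its sign weights also agree with Table 1: 41.7% x (24, 40, 20, 16%) = 10.0, 16.7, 8.3, 6.7%. Tables 1 and 2 and the form thus share weights but not levels.

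**The case against.** Section 9.4.2 has licensed practitioners do the scoring, and Appendix 4 is headed a participant questionnaire. They could apply Table 2 directly at the examination. That would give a valid score, but no supplied form has a field for Table 2 levels: the only summary grid, in Appendix 1, holds total and average scores by part. Section 10.1.6.1 says all data points are source data verified, and a level noted nowhere could not be.

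Part of the score does carry over. Cold frequency over two months and aversion map to Table 2 from Appendix 4, and voice would with a one-line rule. A reader might infer that Appendix 4 cannot yield the score at all; that is too strong. The strict failure is pulse and tongue, with sweating partial.

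A reader might also infer that the same answers routinely show improvement under one reading and worsening under the other. The plan never prescribes scoring by position, the form prints no numbers beside the options, and the reversal touches at most two of ten pairs under an assumed match for d. One key applied throughout produces no contradiction.

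Finally, the version date (18 February 2022) against "The enrollment will start in Dec. 2018 and concluded in March 2019" invites the inference that a recode was chosen with data in hand. The documents do not show that any recode exists or when it was fixed. Section 6.3 blinds participants and on-site investigators, and a single conversion fixed while blinded would not by itself favour an arm. It could still misorder change and add noise.

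**Conclusion.** The point holds as a gap in the definition of the primary score. As printed, 35.0% of the weight (tongue and the two pulse items) has no defined value from Appendix 4, and a further 16.7% (sweating) is only partly defined. Voice needs a stated rule. The direction reversals (-0.33 against +0.17, and -0.17 against +0.33) illustrate what the missing rule can do. They rest on scoring by position and on matching d to Table 2 level 2, and are not an established feature of the data.

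The screening form has its own mismatch in scale and recall period, so correcting Appendix 4 alone would not repair the entry score. The range conflict (0 to 3.30 against 1-5) arises from Tables 1 and 2 alone, whatever the forms say; it is a separate defect that leaves the meaning of 1.8 unclear.

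Bias in favour of either arm is not shown. Nor does the form's fit to Attachment I justify making that index the primary score: the V4.0 plan does not name it, and adopting it would replace the endpoint.

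**What to change.** Reconcile Table 2, Appendix 1 and Appendix 4 so that one scoring key serves screening, baseline and follow-up.

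- **If data are still to be collected:** replace the sweating and sign items on both forms with the Table 2 levels, and use the two-month cold recall on both.
- **If data were already collected on these forms:** state one item-by-item conversion to the V4.0 score, covering sweating, both pulse items, tongue, voice and the Appendix 1 items. Give the date it was fixed relative to unblinding. Report an alternative scoring that follows the form's own order and 1-5 ratings (Attachment I levels) as a sensitivity analysis, without replacing the primary score.
- **In either case:** state the true range of the score and the scale on which the 1.8 threshold was derived.

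The cost is a form or scoring-key revision. The stated range must be corrected, and the threshold may have to be restated on the scale it came from.

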## Part III

3. Do you often feel shortness of breath?
4. Do you often feel unwillingness to talk?

## Part IV

1. Do you often feel limb weakness?
2. Do you often feel a lack of energy?
3. Do you often feel in low spirits?

## Part V

1. Do you often have a cough?
2. Do you often have thin sputum
3. Do you often feel timidity

## Part VI

1. Do you often have poor appetite?
2. Do you have loose stools
3. Do you often have uncomfortable feeling in the abdomen after eating?

Part VII

1. Do you often feel palpitations?
2. Do you often feel depressed?

Part VIII

1. Do you have frequency of urination?
2. Do you often feel soreness of lower back?
3. Do you have cold limbs, especially legs?

Part IX

Score (Score each on a 1-5 scale)

5. weak or powerless pulse
6. cun-pulse superficial or weak
7. corpulent tongue or with white fur
8. low voice

# Appendix 5

## Subject Record at Follow-up

PROMIS® Scale v1.2 – Global Health

### Global Health

Please respond to each question or statement by marking one box per row.

		Excellent	Very good	Good	Fair	Poor
Global01	In general, would you say your health is: .....	 5	 4	 3	 2	 1
Global02	In general, would you say your quality of life is: .....	 5	 4	 3	 2	 1
Global03	In general, how would you rate your physical health? .....	 5	 4	 3	 2	 1
Global04	In general, how would you rate your mental health, including your mood and your ability to think? .....	 5	 4	 3	 2	 1
Global05	In general, how would you rate your satisfaction with your social activities and relationships? .....	 5	 4	 3	 2	 1
Global09r	In general, please rate how well you carry out your usual social activities and roles. (This includes activities at home, at work and in your community, and responsibilities as a parent, child, spouse, employee, friend, etc.).....	 5	 4	 3	 2	 1
		Completely	Mostly	Moderately	A little	Not at all
Global06	To what extent are you able to carry out your everyday physical activities such as walking, climbing stairs, carrying groceries, or moving a chair? .....	 5	 4	 3	 2	 1

PROMIS® Scale v1.2 – Global Health

**In the past 7 days...**

		Never	Rarely	Sometimes	Often	Always						
Global10r	How often have you been bothered by emotional problems such as feeling anxious, depressed or irritable? .....	 5	 4	 3	 2	 1						
		None	Mild	Moderate	Severe	Very severe						
Global08r	How would you rate your fatigue on average? .....	 5	 4	 3	 2	 1						
Global07r	How would you rate your pain on average? .....	 0 No pain	 1	 2	 3	 4	 5	 6	 7	 8	 9	 10 Worst pain imaginable

# Appendix 6

## Subject Record at Follow-up

Neuro-QOL Item Bank v1.0 – Emotional and Behavioral Dyscontrol – Short Form

### Emotional and Behavioral Dyscontrol – Short Form

Please respond to each question or statement by marking one box per row.

In the past 7 days...		Never	Rarely	Sometimes	Often	Always
EDMAN042	I had trouble controlling my temper.....	 1	 2	 3	 4	 5
NQPER05	It was hard to control my behavior.....	 1	 2	 3	 4	 5
NQPER06	I said or did things without thinking.....	 1	 2	 3	 4	 5
NQPER07	I got impatient with other people.....	 1	 2	 3	 4	 5
NQPER11	I was irritable around other people.....	 1	 2	 3	 4	 5
NQPER12	I was bothered by little things.....	 1	 2	 3	 4	 5
NQPER17	I became easily upset.....	 1	 2	 3	 4	 5
NQPER19	I was in conflict with others.....	 1	 2	 3	 4	 5

©2008-2018 David Cella and the PROMIS Health Organization on behalf of the National Institute for Neurological Disorders and Stroke (NINDS). Used with permission.

English  
February 19, 2018

Page 1 of 1

## Appendix 7

